7.8.2 Laboratory data

The analyses of laboratory data will be descriptive in nature and will be based on BI standards "Display and Analysis of Laboratory Data" ([10](#)).

Analyses will be based on normalised values, which means transforming to a standard unit and a standard reference range. The original values will be analysed if the transformation into standard unit is not possible for a parameter.

Descriptive statistics of laboratory values over time and for the difference from baseline (see [Section 6.7](#)) will be provided. In addition, median urine and plasma electrolytes over time will be presented graphically. Frequency tables of changes between baseline and last value on treatment with respect to the reference range will be presented.

Possibly clinically significant abnormal laboratory values are only those identified either in the Investigator's comments or at the RPM/DBLM at the latest. It is the Investigator's responsibility to decide whether a lab value is clinically significant abnormal or not. Standard or project-specific rules for flagging clinically significant values in an automated manner will not be applied in this study.

Clinically relevant findings in laboratory data will be reported as baseline conditions (at screening) or as AEs (during the trial) if judged clinically relevant by the investigator, and will be analysed as such.

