**5.2.3 Assessment of safety laboratory parameters**

For the assessment of laboratory parameters, blood and urine samples will be collected by the trial site at the time points indicated in the [Flow Chart](#) after the subjects have fasted for at least 8 h (excluding sample at 06:00h post administration).

If safety laboratory measurement is performed with other blood collection, e.g. PK sampling, safety laboratory measurement will always be performed first, preferably without any tourniquet.

The parameters that will be determined are listed in [Tables 5.2.3: 1](#) and [5.2.3: 2](#). Reference ranges will be provided in the ISF, Section 10.

Manual differential white blood cell count or urine sediment examinations will only be performed if there is an abnormality in the automatic blood cell count or in the urinalysis, respectively.

Table 5.2.3: 1      Routine laboratory tests

Category	Test name	A	B	C
Haematology	Haematocrit	X	X	X
	Haemoglobin	X	X	X
	Red blood cells (RBC)	X	X	X
	White blood cells (WBC)	X	X	X
	Platelets	X	X	X
	Reticulocyte count	X	X	X
Automatic WBC differential (relative and absolute)	Neutrophiles	X	X	X
	Eosinophils	X	X	X
	Basophils	X	X	X
	Monocytes	X	X	X
	Lymphocytes	X	X	X
Manual differential WBC (if automatic differential WBC is abnormal and clinically relevant in the opinion of the investigator)	Polymorphnuclear neutrophils (segs), band neutrophils (stabs), eosinophils, basophils, monocytes, lymphocytes			
Coagulation	Activated partial thromboplastin time (aPTT)	X	X	X
	Prothrombin Time (Quick and INR)	X	X	X
Enzymes	Aspartate aminotransferase (AST/GOT, SGOT)	X	X	X
	Alanine aminotransferase (ALT/GPT, SGPT)	X	X	X
	Alkaline phosphatase	X	X	X
	Gammaglutamyl transferase (GGT)	X	X	X
	Lactate dehydrogenase	X	X	X
	Amylase	X	X	X
	Lipase	X	X	X

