## **Trial Protocol**

19 Feb 2018

Page 48 of 82

Proprietary confidential information © 2018 Boehringer Ingelheim International GmbH or one or more of its affiliated companies

Table 5.2.3: 1 Routine laboratory tests (cont'd)

Category	Test name	A 	B 	C 
Substrates	Glucose (plasma)	X	-	-
	Creatinine	X	X	X
	eGFR, calculated from serum creatinine using CKD-EPI formula	X	X	X
	Bilirubin, total	X	X	X
	Bilirubin, direct	X	X	X
	Cholesterol, total	X	X	X
	Triglycerides	X	X	X
	C-reactive protein	X	X	X
	Urea	X	X	X
Electrolytes	Calcium	X	X	X
	Sodium	X	X	X
	Potassium	X	X	X
	Chloride	X	X	X
Hormones	Thyroid stimulating hormone (TSH)	X	-	-
	*Aldosterone	-	X	-
0-4h and 0-24h collection Urine**	Urine potassium	-	X	-
	Urine sodium	-	X	-
	Urine chloride	-	X	-
	Urine creatinine	-	X	-
	Potassium-creatinine-quotient	-	X	-
	Sodium-creatinine-quotient	-	X	-
Urinalysis (Stix) [Urin-Sediment will be performed , if urinalysis abnormal]	Urine nitrite	X	X	X
	Urine protein	X	X	X
	Urine glucose	X	X	X
	Urine ketone	X	X	X
	Urobilinogen	X	X	X
	Urine bilirubin	X	X	X
	Urine RBC	X	X	X
	Urine WBC	X	X	X
	Urine pH	X	X	X
Urine sediment (microscopic examination if erythrocytes, leukocytes nitrite or protein are abnormal in urine)	Only positive findings will be reported (for instance, the presence of sediment bacteria, casts in sediment, squamous epithelial cells, erythrocytes, leukocytes)			

A: parameters to be determined at screening examination

B: parameters to be determined during the study (for time points refer to [Flow Chart](#))

C: parameters to be determined during the Follow-up-examination

\* Aldosterone (after a 15-minute resting period in supine position) samples may be stored at about -20C in case shipment/analytic on the same day is not possible

\*\* For baseline from blank urine sample (planned time -1:30), urine collected 0-4h and all Urine collected from 0-24h. These will be stored intermittent in a refrigerator. After processing the 12-24h PK urine fraction (cf. [Section 5.5.2.3](#)), all collected fractions (0-24h) will be mixed for the 24h urine electrolyte measurement. Mixing should be done by transferring the entire content of all collection containers into a single PE/PP or glass

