**5.2.5.2 Medical examinations**

At screening, the medical examination will include demographics including height and body weight, smoking and alcohol history, relevant medical history and concomitant therapy, review of inclusion and exclusion criteria, review of vital signs (BP, PR), 12-lead ECG, laboratory tests, and a physical examination. At the end of trial examination, it will include review of vital signs, 12-lead ECG, laboratory tests, and a physical examination.

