**16.1.1 Protocol and amendments**

---

Proprietary confidential information © 2018 Boehringer Ingelheim International GmbH or one or more of its affiliated companies**Boehringer Ingelheim****BI Trial No.: 1399-0001****c15848245-03****Trial Protocol****19 Feb 2018****Page 62 of 82**

---

Proprietary confidential information © 2018 Boehringer Ingelheim International GmbH or one or more of its affiliated companies**7.3.3 Safety analyses**

Safety will be assessed for the endpoints listed in [Section 5.2.1](#). All treated subjects (that is, all subjects who received at least one dose of study drug), will be included in the safety analysis. Safety analyses will be descriptive in nature and will be based on BI standards. No hypothesis testing is planned.

Treatments will be compared in a descriptive way. The placebo control group in the safety evaluation will consist of all placebo treated subjects, regardless of the dose group in which they were treated. The active treatment groups will be compared to the placebo group in a descriptive way. Tabulations of frequencies/proportions will be used for the evaluation of categorical (qualitative) data, and tabulations of descriptive statistics will be used to analyse continuous (quantitative) data.

The analyses will be done by 'treatment at onset'.

Measurements (such as ECG, vital signs, or laboratory parameters) or AEs will be assigned to treatments (see [Section 4.1](#)) based on the actual treatment at the planned time of the measurement or on the recorded time of AE onset (concept of treatment emergent AEs). Therefore, measurements planned or AEs recorded prior to first intake of trial medication will be assigned to 'screening', those between first trial medication intake until the trial termination date will be assigned to the treatment period. These assignments including the corresponding time intervals will be defined in detail in the TSAP.

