**Trial Protocol**

**19 Feb 2018**

**Page 63 of 82**

Proprietary confidential information © 2018 Boehringer Ingelheim International GmbH or one or more of its affiliated companies

Additionally, further treatment intervals (analysing treatments) may be defined in order to provide summary statistics for time intervals, such as combined treatments, on-treatment totals or periods without treatment effects (such as screening).

Adverse events will be coded using the Medical Dictionary for Regulatory Activities (MedDRA). Frequency, severity and causal relationship of AEs will be tabulated by treatment, system organ class and preferred term. SAEs, AESIs (see [Section 5.2.2.1](#)) and other significant AEs (according to ICH E3) will be listed separately.

Laboratory data will be compared to their reference ranges. Values outside the reference range will be flagged in the listings. Additionally, differences from baseline will be evaluated.

For vital signs and the differences from baseline will be evaluated. Additionally, plots over the time will be provided for spirometry data.

A centralised evaluation of all 12-lead ECGs recordings (see [Section 5.2.4](#)) will be the basis for the derivation of further ECG parameters based on the ECG variables QT, HR, QTcF, QTcB, PR, QRS, and RR. The baseline value of an ECG variable is defined as the mean of the triple ECG measurements prior to drug administration. The derivation of the quantitative and qualitative ECG endpoints and their analyses will be described in the TSAP.

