6. GENERAL ANALYSIS DEFINITIONS

6.1 TREATMENTS

For basic study information on treatments to be administered, assignment of treatment groups, and selection of doses, cf. Section 4 of the CTP.

Subjects were planned to be treated either with

- a single dose of 3, 10, 30, 100, 300, 600, or 1200 µg of BI 1265162 (test treatments)
or
- a single dose of placebo (reference treatment)

All placebo subjects will be analysed in one pooled placebo group (i.e. no distinction between dose groups will be made for placebo subjects).

Analysis phases for statistical analysis of AEs, safety laboratory data, vital signs, and ECG are defined for each subject as described in the table below.

Table 6.1: 1 Flow chart of analysis phases for statistical analyses of AEs, safety laboratory data, vital signs, and ECG

Study analysis phase	Label	Start (inclusive)	End (exclusive)
Screening	Screening	Date of informed consent	Date/time of first administration of study drug
On-treatment	Pbo, 3 ug BI, 10 ug BI, 30 ug BI, 100 ug BI, 300 ug BI, 600 ug BI, or 1200 ug BI, respectively	Date/time of administration of study drug	12:00 a.m. on day after subject's trial termination date

CTR Section 15, Appendix 16.1.13.1.8.2 and Appendix 16.1.13.1.8.3 AE displays will present results for the on-treatment phase only.

In CTR Section 15 AE tables (but not in Appendix 16.1.13.1.8.2 and Appendix 16.1.13.1.8.3 AE tables), the following totals will be provided in addition:

- "**Total BI**", defined as the total over all on-treatment phases involving BI
- "**Total on-trt**", defined as the total over all on-treatment phases, including placebo

CTR Appendix 16.1.13.1.8.1 displays will present results for the screening and on-treatment phases.

Additionally to the totals defined above, the following total will be provided in CTR Section 16.1.13.1.8.1 AE tables:

- "Total", defined as the total over all study phases (screening + on-treatment)

More details on the technical implementation of these analyses are provided in the ADS Plan of this TSAP.

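### In the visible text of SAP 7.8.2, the only laboratory count against the reference range uses the last on-treatment value, which after a single dose is mostly the end-of-trial sample

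*SAP*

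**What the plan says.** SAP 7.8.2 plans descriptive statistics of laboratory values over time and of differences from baseline, median plots of urine and plasma electrolytes, and one table counted against the reference range: "Frequency tables of changes between baseline and last value on treatment with respect to the reference range will be presented". It also says: "Standard or project-specific rules for flagging clinically significant values in an automated manner will not be applied in this study". Possibly clinically significant values are those named in the investigator's comments or at the report planning meeting. A laboratory finding becomes an adverse event (AE) if the investigator judges it clinically relevant.

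SAP Table 6.1: 1 ends the on-treatment phase at "12:00 a.m. on day after" the subject's trial termination date. Protocol 7.3.3 agrees: "those between first trial medication intake until the trial termination date will be assigned to the treatment period".

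The end-of-trial sample falls inside that phase. Protocol 5.2.5.2 says "At the end of trial examination, it will include review of vital signs, 12-lead ECG, laboratory tests, and a physical examination", and column C of Table 5.2.3: 1 holds the "parameters to be determined during the Follow-up-examination". Earlier post-dose samples exist. The fasting rule in protocol 5.2.3 names one by "excluding sample at 06:00h post administration".

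On display, protocol 7.3.3 says: "Laboratory data will be compared to their reference ranges. Values outside the reference range will be flagged in the listings". SAP 7 lists all individual values and puts minimum and maximum in every summary table of continuous variables.

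**The concern.** Each subject receives one dose. A laboratory effect of that dose may appear within hours and be gone by the end-of-trial visit. A table built on the last value then describes recovery, not what happened after dosing, for every parameter that is sampled again at end of trial.

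The other route to a count is the AE tables, which depend on the investigator's judgement of clinical relevance. Protocol 4.1.5.1 blinds subjects only, 4.1.2 gives the site the allocation list in advance, and 3.2 itself acknowledges possible observer bias on dose-dependent effects. A count against the reference range does not rest on that judgement, so it matters which sample it uses.

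What is at stake is a descriptive comparison of each dose with placebo, which protocol 7.1.1 sets as the way safety is investigated. Serum potassium is among the parameters concerned, and protocol 4.2.1 gives hyperkalaemia as an example of an AE that may need treatment.

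**Working it through.** The plan gives no figure for this point. The check counts rows of Table 5.2.3: 1 in the revised protocol (19 February 2018) and then works out the background count that the fix would bring.

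**1. Which rows have an end-of-trial sample**

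- Column B (measured during the study), without dipstick tests: haematology 6 + differential 5 + coagulation 2 + enzymes 7 + substrates 8 (plasma glucose is screening only) + serum electrolytes 4 + aldosterone 1 + collected urine 6 = 39.
- Of these, rows also in column C (follow-up examination): 6 + 5 + 2 + 7 + 8 + 4 = 32. Aldosterone and the 6 collected-urine rows are the 7 without.
- Share: 32/39 = 82%. With the 9 dipstick rows, which are in both columns, it is 41/48 = 85%.

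For these rows, the last on-treatment value of a subject who attends the end-of-trial visit is the sample taken then, unless a later repeat precedes trial termination. Earlier post-dose samples do not enter the table.

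**2. Background count with a worst-value table**

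Inputs from the documents: 7 doses, 6 active subjects per dose, 7 × 2 = 14 pooled placebo subjects. Inputs that are assumptions, because the Flow Chart is not shown and no background rate is given: a proportion r = 0.01 to 0.05 of samples out of range with no drug effect, half low and half high; k = 2 to 4 independent post-dose samples.

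- Last value, per direction: r/2 = 0.005 to 0.025.
- Worst value, per direction: b = 1 − (1 − r/2)^k. Low: 1 − 0.995² = 0.0100. High: 1 − 0.975⁴ = 0.0963.
- Chance of 2 or more of 6 subjects out of range: P = 1 − (1 − b)⁶ − 6b(1 − b)⁵ = 0.00145 to 0.107. For the last value, the same formula with r/2 gives 0.00037 to 0.0088.

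The number of cells depends on how measures are counted (measures × 7 doses × 2 directions):

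| Measures counted | Cells | Chance cells, worst value |
|---|---|---|
| 32 table rows | 448 | 0.7 to 48 |
| 38, with relative and absolute differential (+5) and Quick and INR (+1) separate | 532 | 0.8 to 57 |
| 45, if aldosterone and the 6 collected-urine rows also have ranges | 630 | 0.9 to 67 |

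Dipstick tests would add up to 9 × 7 = 63 cells. The last-value table gives 0.2 to 3.9 chance cells on the 448-cell count. The expected pooled placebo count per measure and direction with the worst value is 14b = 0.14 to 1.35. Positive correlation between a subject's samples would lower b. Some reference ranges may be one-sided, which would lower the cell counts.

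**The case against.** The strongest reply is that the visible text is not the whole plan. SAP 7.8.2 rests on the sponsor's laboratory standard (SAP reference 10), which cannot be seen. The SAP contents list also passes from 7.8.4 to 7.8.7, and 7.8.4 cites an additional Section 9.2 that is not shown. A worst-value table may exist in any of these. This stands as a limit: the point can be made only about the visible text.

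Second, little is hidden. For each numeric parameter, dose and time point, the minimum and maximum can be set against the standard reference range to see whether anyone left it. Listings are sorted by dose group and flag out-of-range values, with 6 active subjects per dose. Reported AEs, other significant AEs (which include marked laboratory abnormalities) and hepatic-injury events are tabulated whether or not they resolve. This also stands. A reader might infer that transient changes are lost to the report. They are not. What is missing is the tally of subjects by dose.

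Third, no commitment is broken. Protocol 7.3.3 promises comparison with reference ranges, flags in listings and differences from baseline, and all are planned. The point is therefore an improvement, not a contradiction between the documents.

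Fourth, the fix adds noise, by roughly a factor of twelve at the upper inputs (3.9 to 48 on 448 cells). That is true, and it governs how the tables are read.

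**Conclusion.** The point holds for the visible text. The one laboratory table counted against the reference range shows end-of-trial status for 32 of 39 non-dipstick rows, in subjects who attend that visit. Subjects who left the range and recovered without a reported AE are not counted by dose against pooled placebo in any table described there. Severity is minor.

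Three stronger inferences are not supported:

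- **32 of 39 as a measure of lost information.** It counts parameters with an end-of-trial sample. The documents give no rate of transient changes and do not show which parameters are sampled at 6 h.
- **Amendment 1 as evidence.** Its interest in early changes concerns urine electrolytes, which have no end-of-trial sample and lie outside the 32 rows.
- **An effect on the main conclusions.** The primary endpoint counts subjects with drug-related AEs, and the escalation reviews in protocol 3.1 look at the laboratory tests themselves. Neither uses this table.

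The conclusion rests on attendance at the end-of-trial visit and on no further display being required by reference 10 or by redacted SAP text.

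**What to change.** Add to SAP 7.8.2:

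*Shift tables with respect to the reference range will also be given from baseline to the minimum and from baseline to the maximum scheduled post-dose value for numeric parameters with a reference range, and from baseline to the worst post-dose category for dipstick tests. They will be shown by dose group and pooled placebo, are descriptive, and are to be read against pooled placebo.*

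Keep the last-value table, with a footnote that it shows end-of-trial status where an end-of-trial sample exists. If reference 10 or another SAP section already requires such tables, one sentence in 7.8.2 saying so closes the point.

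The cost is a few lines of text and extra tables from data already collected. The downside is the higher background count shown above. Isolated cells with 2 of 6 subjects out of range should not be taken as signals on their own. Pooled placebo is the yardstick, provided its subjects are sampled on the same schedule.

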7.8.3 Vital signs

The analyses of vital signs (blood pressure and pulse rate) will be descriptive in nature. Descriptive statistics of vital signs over time and for the difference from baseline (see [Section 6.7](#)) will be provided.

Clinically relevant findings in vital signs data will be reported as baseline conditions (at screening) or as AEs (during the trial) if judged clinically relevant by the investigator, and will be analysed as such.

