**3. DESCRIPTION OF DESIGN AND TRIAL POPULATION**

**3.1 OVERALL TRIAL DESIGN AND PLAN**

This single-rising dose trial is designed as single-blind, partially randomised, and placebo-controlled within parallel dose groups.

Partially randomised means that the subjects will be treated in two equally sized cohorts per dose group, with the first cohort being treated in a fixed sequence and the second cohort being treated in a randomised order.

A total of 56 healthy male subjects is planned to participate in the trial, according to 7 sequential groups comprising 8 subjects per group. However, additional subjects may be entered to allow testing of intermediate doses within the planned and approved dose range on the basis of experience gained during trial conduct (e.g. preliminary PK data), i.e. the actual number of subjects entered may exceed 56. Such changes may be implemented via non-substantial CTP Amendments.

Within each dose group, 6 subjects will receive the active drug and 2 will receive placebo. Only one dose is tested within each dose group

The dose groups to be evaluated are outlined in [Table 3.1: 1](#) below.

---

---

---

On the first study day of each dose level, the first cohort will be treated in the following order: first subject (active) followed at least 1 h later by the second subject (placebo) followed at least 1 h later by the third subject (active) followed at least 10 min later by the fourth subject (active). If BI 1265162 treatment is safe and showed acceptable tolerability in the first cohort, the subjects in the second cohort will be treated not earlier than 2 days later than the first treated volunteer in the first cohort. In the second cohort, a time interval of at least 10 min will be maintained between dosing of individual subjects in a random order. The dose groups will be investigated consecutively in ascending order of doses. A time interval of at least 6 days will be maintained between the administration of the study drug to the first cohort in a dose group and the first cohort in the next dose group. The decision to proceed to the next dose group will be based upon the safety, tolerability data of the preceding dose groups and explorative PK data in some dose groups (see [Section 7.3.4](#)).

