**7.2 NULL AND ALTERNATIVE HYPOTHESES**

Safety and tolerability of the different dose groups of BI 1265162 are to be determined on the basis of the investigated parameters in comparison to placebo. It is not planned to test any statistical hypotheses with regard to these variables in a confirmatory sense. Instead, they will be described in their entirety and evaluated by descriptive statistical methods.

Confidence intervals will be computed and will have to be interpreted in the perspective of the exploratory character of the study, i.e. confidence intervals are considered as interval estimates for effects.

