**7.6 DETERMINATION OF SAMPLE SIZE**

It is planned to include a total of 56 subjects in this trial. The planned sample size is not based on a power calculation. The size of 8 subjects per dose group (6 on active treatment, and 2 on placebo) is commonly used in single-rising dose studies of the present type and is in general considered as sufficient for the exploratory evaluation of single dose safety and pharmacokinetics [[R95-0013](#)].

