7.8.4 ECG

12-lead ECG

Abnormal findings will be reported as baseline conditions (at screening) or as AEs (during the trial) if judged clinically relevant by the investigator.

All evaluation of ECG data will be based on the TS.

Listing of individual data

For all quantitative endpoints, listings of individual data will be shown in Appendix 16.2. Occurrences of notable findings will be flagged.

For all subjects with any notable finding in quantitative ECG recordings, a separate listing will be created as end-of-text display (based on the same display template as in Appendix 16.2), and the corresponding time profiles will be shown.

Comments regarding the ECGs will be listed.

Analysis of central tendency

Descriptive statistics (N, mean, SD, min, median, max) will be provided for the changes from baseline over time in all ECG variables.

For QTcF, QT and HR, a repeated measurements analysis of the changes from baseline with baseline as a covariate will be performed. The model will include the fixed effects "baseline", "treatment", "time", "baseline*time" interaction, and "treatment*time" interaction. The covariance model for the repeated effect "time" will be unstructured (i.e. TYPE=UN or UNR); in case of convergence problems refer to [Additional Section 9.2](#). For each dose group and each time point, the contrast of the means for "treatment-placebo" will be estimated by the difference in the corresponding adjusted means (Least Squares Means); two-sided 90% CIs based on the t-distribution will also be computed. For each of the above ECG variables, the time profiles of the mean differences to placebo in the changes from baseline and the corresponding 90% CIs will be presented in a figure.

The following SAS code can be used to fit the model:

```
PROC MIXED DATA=indata CL METHOD=REML;
  CLASS subject treat time;
  MODEL ECGep = treat time base treat*time base*time / DDFM=KR CL ALPHA=0.1;
  REPEATED time / TYPE=UN SUBJECT=subject;
  LSMEANS treat*time / DIFF CL ALPHA=0.1;
  SLICE treat*time / SLICEBY=time DIFF CL ALPHA=0.1 NOF PLOT=none;
  RUN;
```

For PR, QRS, RR as well as QTcB, the time profiles of mean and SD for the changes from baseline on treatment will be displayed graphically by treatment.

Categorical Endpoints

For the categorical endpoints, frequency tables will be provided.

For subjects with notable findings, the individual time courses of QTcF, QT, HR, PR and QRS of these subjects will be presented in figures.

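### Blood pressure and plasma electrolytes are summarised as raw changes with no placebo contrast or interval, although the SAP's ECG model could supply a baseline-adjusted one at little cost

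*SAP*

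**What the plan says.** Protocol 7.2 takes placebo as the reference and sets the aim: "Safety and tolerability of the different dose groups of BI 1265162 are to be determined on the basis of the investigated parameters in comparison to" that reference. It plans no confirmatory test and relies on descriptive methods. It also says that confidence intervals will be computed and read as exploratory interval estimates of effects.

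The SAP then treats the safety variables in two ways.

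- **Vital signs (SAP 7.8.3):** "The analyses of vital signs (blood pressure and pulse rate) will be descriptive in nature". Values over time and differences from baseline are tabulated.
- **Laboratory data (SAP 7.8.2):** "Descriptive statistics of laboratory values over time and for the difference from baseline" are given, with plots of median urine and plasma electrolytes over time and tables of change relative to the reference range.
- **ECG (SAP 7.8.4):** "For QTcF, QT and HR, a repeated measurements analysis of the changes from baseline with baseline as a covariate will be performed". The model has baseline, treatment, time, baseline by time and treatment by time. It reports dose minus placebo with two-sided 90% intervals, and SAS code is supplied. PR, QRS, RR and QTcB get unadjusted changes only.

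The comparator is common to all: "All placebo subjects will be analysed in one pooled placebo group" (SAP 6.1).

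**The concern.** The question for blood pressure and potassium is the same as for QTcF: how does each dose differ from placebo, and how precisely is that known? For QTcF the SAP answers it. For blood pressure and electrolytes the reader must subtract two group means by eye, with no standard error.

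With six subjects in a dose group, its mean baseline will often differ from that of placebo. A raw change removes only part of the difference. The rest returns as regression to the mean: a group that starts high tends to fall relative to placebo, and a group that starts low tends to rise. That can add to a dose effect or hide part of one. The median electrolyte plots show values rather than changes, so they carry the whole baseline difference.

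Two features make the point more relevant here. Outside the ECG, baseline is the last single value before dosing (SAP 6.7), whereas the ECG baseline is the mean of a triplicate; a noisier baseline lowers the correlation with later values. And the plan itself treats electrolytes as important: the protocol names hyperkalaemia as its example of an adverse event needing treatment (4.2.1), aldosterone is measured, and Amendment 1 added an early urine electrolyte measurement.

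**Working it through.** **Inputs from the documents.** "Within each dose group, 6 subjects will receive the active drug and 2 will receive placebo" and "according to 7 sequential groups comprising 8 subjects per group" (protocol 3.1). Hence 7 × (6 + 2) = 56, which reproduces the planned total, and the pooled placebo group has 7 × 2 = 14. There is no power calculation to reproduce: "The planned sample size is not based on a power calculation" (protocol 7.6).

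**Assumptions.** The documents give no SD for these variables and no correlation rho between baseline and post-dose values. I take equal variances before and after dosing, work in SD units and show rho from 0.4 to 0.8.

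**Formulas**, with k = √(1/6 + 1/14) = 0.488:

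- SD of the baseline difference, one dose against placebo: k.
- Shift of the raw-change contrast for a baseline difference D: −(1 − rho) × D.
- SE of the raw-change contrast: k√(2(1 − rho)).
- SE of the baseline-adjusted contrast, large-sample: k√(1 − rho²).
- Share of the raw-change variance due to imbalance: (1 − rho)²k² / [2(1 − rho)k²] = (1 − rho)/2.
- Relative narrowing from adjustment: 1 − √((1 + rho)/2).

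| rho | Shift for a one-SD (0.488) imbalance | SE, raw change | SE, adjusted | Variance share | Narrowing, theory | Narrowing, simulated |
|---|---|---|---|---|---|---|
| 0.4 | 0.293 | 0.535 | 0.447 | 30% | 16% | 15% |
| 0.5 | 0.244 | 0.488 | 0.423 | 25% | 13% | 12% |
| 0.6 | 0.195 | 0.436 | 0.390 | 20% | 11% | 10% |
| 0.7 | 0.146 | 0.378 | 0.348 | 15% | 8% | 7% |
| 0.8 | 0.098 | 0.309 | 0.293 | 10% | 5% | 4% |

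The simulated column estimates the baseline slope from 14 placebo subjects and seven groups of six with no drug effect, so it falls slightly short of theory.

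**In clinical units.** With an assumed SD of 10 mmHg, a one-SD imbalance is 4.9 mmHg. It shifts the raw-change contrast by 2.9, 2.0 or 1.0 mmHg for rho 0.4, 0.6 or 0.8. At rho 0.6 the 90% half-width (normal approximation) is 1.645 × 4.36 = 7.2 mmHg for raw change and 1.645 × 3.90 = 6.4 mmHg adjusted. With an assumed potassium SD of 0.3 mmol/L, the imbalance is 0.15 mmol/L and the shift is 0.09, 0.06 or 0.03 mmol/L.

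**Average and conditional behaviour.** Over all simulated trials the mean raw-change contrast is about 0. Among doses whose baseline exceeds placebo by more than 0.5 SD, the mean raw-change contrast is −0.375, −0.223 and −0.153 SD for rho 0.5, 0.7 and 0.8. The adjusted contrast is within 0.003 SD of zero in each case.

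**The case against.** A reader might infer that chance imbalance will produce false dose effects and that the covariate would prevent them. The documents and the arithmetic do not support this.

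- The chance that imbalance alone shifts at least one of seven doses by 3 mmHg or more (SD 10) runs from 89% at rho 0.4 to 1.5% at rho 0.8. With no rho in the documents, no single figure can be quoted.
- Once ordinary sampling error is included, the fix barely changes that risk. At rho 0.6 the chance that some dose differs from placebo by at least 3 mmHg with no drug effect is about 99% for raw change and 98% after adjustment. The driver is six subjects per dose.
- The shift is smaller than sampling error at every rho tried.

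The sponsor can also say that the SAP follows the protocol, whose safety comparison is descriptive and untested (7.2, 7.3.3). The visible text ties no decision rule to these mean changes. Baseline differences can be seen, because observed values over time are tabulated and individual data listed. Four ECG variables go unadjusted too. Pulse rate is largely covered, since protocol 5.2.5.1 equates it with heart rate and HR is modelled. Parts of the SAP are not visible (numbering runs from 7.8.4 to 7.8.7, and Section 9 is absent), so a further analysis cannot be ruled out.

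All of this stands, and it limits the point to a modest one. It does not remove it. The ECG model is equally exploratory, yet the SAP uses it to give a placebo contrast and an interval, while the readable text of 7.8.2 and 7.8.3 gives neither.

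**Conclusion.** The point holds as a proportionate improvement. For blood pressure and plasma electrolytes the visible SAP lacks the estimate that best matches the protocol's question: dose minus placebo, with an interval. Raw change is a valid summary and is unbiased on average under chance imbalance. It is less precise, and it is shifted in any given group whose baseline happens to differ.

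Adjustment removes that conditional shift and narrows the contrast by about 4–15% for rho 0.8–0.4. Imbalance accounts for 10–30% of the raw-change variance over the same range. These figures rest on assumed rho and equal variances; the mmHg and mmol/L values also rest on assumed SDs.

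Chance is not the only source of imbalance. Subjects join dose groups according to when they can attend (protocol 4.1.2), and the first cohort at each dose is not randomised (protocol 7.5). A covariate handles a measured baseline difference but not a period effect between dose groups.

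**What to change.** In SAP 7.8.2 and 7.8.3 add, as a supportive exploratory analysis, the 7.8.4 model (change from baseline on baseline, treatment, time, baseline by time and treatment by time) for:

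- systolic and diastolic blood pressure;
- plasma potassium and sodium;
- optionally, pulse rate and log-transformed aldosterone.

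Use each variable's own planned times. Report adjusted dose-minus-pooled-placebo means with two-sided 90% intervals beside the descriptive tables, labelled exploratory in the sense of protocol 7.2. State what happens if the unstructured covariance does not converge; 7.8.4 already points to an additional section for this.

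Leave urine electrolytes out. Their baseline is a pre-dose blank sample, while post-dose values come from 0–4 h and 0–24 h collections (protocol 5.2.3), so change from baseline does not compare like with like.

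The cost is some SAP wording, reuse of existing code and four to six more tables or figures. No new data are needed. The drawback is more exploratory intervals without multiplicity control. The Flow Chart is not visible, so the number of time points for these models could not be checked here.
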